# **Study Synopsis**

Study Title	Monitoring and evaluation of the therapeutic efficacy and safety of
	pyronaridine-artesunate for the treatment of uncomplicated falciparum
	malaria in western Cambodia, an area of artemisinin-resistant
	falciparum malaria
Background	Emerging resistance to artemisinins and to its partner drugs severely
	threaten the treatment of falciparum malaria in Western Cambodia. To
	inform drug policy, it is crucial to have information on the current
	efficacy of pyronaridine-artesunate, considered as a new first-line
	treatment in Western Cambodia. Pyronaridine-artesunate is a newer
	artemisinin combination therapy, and was recently approved by the
	European Medicine Agency for single time use in adults and children
	>20 kg in countries with documented artemisinin resistance including
	Cambodia, where the drug was tested in 2005 and 2008. We here
	propose an open-labelled clinical trial to assess the efficacy and safety
	of pyronaridine-artesunate for the treatment of uncomplicated
	falciparum malaria or mixed infection in Pailin, Battambang and Pursat
	provinces in Western Cambodia.
Study Design	Observational study for the assessment of drug efficacy and safety over
	42 days
Participants	Patients with acute uncomplicated P. falciparum malaria or mixed with
	another species.
Study sites	Referral hospital (Pailin), Promoy Health Centre (Pursat) and Tasanh
	Health Centre, Battambang.
Sample size	145 patients
Inclusion Criteria	Adults and children ≥ 20 kg
	Symptomatic of malaria infection, i.e. history of fever within 24 hours
	and/or presence of fever >37.5°c.
	Microscopic confirmation of asexual stages of P.falciparum (mixed
	with non-falciparum species in Palin only)
	Capability of taking an oral medication
	Written informed consent given to participate in the trial

	Willingness and ability to adhere to follow-up visit schedule			
Exclusion Criteria	o Pregnancy or lactation (urine test for β HCG to be performed			
	on any woman of child bearing age, that is 18 to 45 y/o)			
	o Female aged 12-18y			
	$\circ$ Parasitemia > 150 000/ $\mu$ L).			
	
 
Signs or symptoms indicative of severe malaria:
 
			
	- Impaired consciousness (Blantyre Coma Score <5)			
	- Severe anaemia (Hct<15%)			
	- Bleeding disorder –evidenced by epistaxis, bleeding gums, frank haematuria, bleeding from venepuncture sites			
	- Respiratory distress			
	- Severe jaundice			
	o Known hypersensitivity to artemisinins - defined as history of			
	erythroderma/other severe cutaneous reaction, angioedema or to pyronaridine			
	
 
History of splenectomy
 
			
	o Patients taking any drug which is known to be metabolised by			
	the cytochrome enzyme CYP2D6 including flecainide,			
	metoprol, imipramine, amitriptyline, clomipramine.			
	o Known history or evidence of clinically significant disorders,			
	such as:			
	o Known active Hepatitis A, e.g. by detection of anti HAV-IgM.			
	- Known hepatitis B surface antigen (HBsAg) carrier.			
	- Known hepatitis C antibody (HCV Ab).			
	
 
Liver function tests (AST/ALT levels) more than 2.5 times the upper limit of normal range.
 
			
Study Period	8 months (May 2014 – December 2014)			
Primary Objective	To assess the therapeutic efficacy of pyronaridine-artesunate for the			
	treatment of uncomplicated falciparum malaria or mixed infection (in Pailin only) at Day 28 and 42, in an area of artemisinin resistance.			

Secondary	Main secondary objectives:
Objectives	To measure the clinical and parasitological efficacy of
Objectives	pyronaridine-artesunate for the treatment of uncomplicated
	P.falciparum and mixed (in Pailin only)
	
 
To determine the polymorphism of molecular markers of P
 

	falciparum resistance (K13, pfmdr1 and copy number)
Primary endpoint	28 day and 42 day PCR corrected ACPR
Secondary	Main secondary endpoint:
Endpoints	
Enapoints	Absolute values and change from baseline related to hepatic
	biological values (ALT, AST, Total and conjugated bilirubin
	and alkaline phosphatase) at day0, day 3, day 7 and day 28
	including any follow up values to confirm return to baseline
	values
	Other secondary endpoints
	• The numbers of patients with a positive malaria slide 72 hours
	after treatment initiation in each group
	• Fever clearance time (i.e. the time taken for tympanic
	temperature to fall below 37.5°C and remain there for at least 24 hours)
	
 
Kaplan Meier analysis over 42 days for recrudescences and reinfections
 

	PCR uncorrected ACPR at D28 and D42
	• 28 day or 42 day PCR corrected ACPR
	Gametocyte carriage rates and gametocyte clearance times in
	each treatment arm
	Documented AEs and SAEs and relationships to study drugs.
	Adverse events in both study arms
	Changes in haematological and biochemical parameters over
	time.
Drugs	Pyronaridine-artesunate (Pyramax®)

# 1. Background

Artemisinin resistance in *Plasmodium falciparum* has emerged in western Cambodia. To date this has been manifest by prolonged parasite clearance rates following treatment with artemisinin derivatives ([name] et al, 2009). There is concern that the efficacy of the artemisinin based combination therapies may be waning in this area due to the development of resistance to the partner drug. A high failure rate following artemether-lumefantrine treatment was first documented in 2006 ([name], 2006), and in 2011 cure rates in a small number of patients in Pailin treated with dihydroartemisinin piperaquine (DHA-PQP) were only 75% ([name], 2012). High 42-day failure rates are now being observed in Pursat province (unpublished CNM data).

Pyronaridine-artesunate (PYR-AS) could be an alternative option for the treatment of uncomplicated falciparum malaria in western Cambodia. On 16 February 2012, the European Medicine Agency (according to Article 58) adopted a positive scientific opinion for pyronaridine-artesunate (Pyramax) 180mg/60mg for the treatment of acute, uncomplicated malaria infection caused by Plasmodium species in adults and children weighing 20 kg or more, in areas of low transmission with evidence of artemisinin resistance (including Cambodia) as a single treatment course. It has been pre-qualified by the WHO.

Pyronaridine -rtesunate (PYAS) was first used as a fixed combination in 2005 in the context of the Phase II development; it is however not yet commercially available in Cambodia. In a RCT multi-centre trial there was a 10% recrudescence rate on D42 in the 211 patients recruited at the western Cambodian site treated with PYAS which contrasted with the overall D42 genotyping corrected efficacy rate of the ACT in the trial of 99.2% (Rueangweerayut et al 2012). The parasite clearnace time was also slower for PYAS in Pailin. It is very important for CNM to verify whether this was a chance finding or if this reflects a genuinely lower efficacy of this treatment in areas where artemisinin resistance is prevalent. The results of this study will inform the National Malaria Treatment Guidelines.

# 2. Study objectives

Primary Objective:

To assess the therapeutic efficacy of pyronaridine-artesunate for the treatment of uncomplicated falciparum malaria or mixed infection (PF+ a non-falciparum species) at Day 42, in an area of artemisinin resistance.

# Secondary Objectives:

- To measure the clinical and parasitological efficacy of pyronaridine-artesunate for the treatment of uncomplicated *P.falciparum* and mixed (in Pailin)
- To determine the polymorphism of molecular markers of *P falciparum*

#### 3. Study endpoints

The primary endpoint of the study is D28 PCR and D42 PCR corrected ACPR to assess therapeutic efficacy pyronaridine artesunate for the treatment of uncomplicated falciparum malaria in an area where artemisinin resistant malaria is prevalent.

# Main secondary endpoints:

• Absolute values and change from baseline related to hepatic biological values (ALT, AST, Total and conjugated bilirubin, alkaline phosphatase and any other relevant parameters if available) at day 0, 3, day 7 and day 28 and where available, any additional follow up values to confirm return to baseline values.

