#### 6. Enrolment procedures

All subjects enrolled in the study will be given a unique code. A case-record form will be completed with each patient documenting symptoms prior to clinic attendance, concomitant illness, drug history. Height, weight, vital signs and physical examination findings will be recorded.

At inclusion all patients will have the following samples taken (total volume for adults  $\geq$ 16 years old: 5 ml; total volume for children under 16 years old: 3 ml).

• Malaria blood film (thick and thin) and haematocrit: 0.5ml

- Filter paper blood blots (3 dots on Whatman 3MM; approx 220-300 uL blood) for PCR parasite genotyping (msp1, msp2, glurp in case of recurrence during follow-up and polymorphism of drug resistance marker)
- Biochemistry analysis: (1 ml) (AST/ALT, bilirubin total/conjugated, alkaline phosphatase)

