# 9. Follow up (see table 1 in appendix)

- All patients will have a blood smear examined daily during the first week by microscopy until parasite clearance (2 consecutive negative slides on two consecutive days; both asexual and sexual stages). A negative blood slide will be defined as parasite count negative per 1000 WBC in two consecutive days. The sample on day 3 will be taken as close as possible to 72h after the initial blood smear.
- Blood biochemistry and basic haematology on D0, D3, D7 D14, D28 and D42. Tests for: AST/ALT, total bilirubin and alkaline phosphatase. If values increase, a confirmation test will be done within 48 hours where practical and clinically indicated. Regarding liver function tests (LFT), any elevation of ALTx3ULN on day 3 not having returned to baseline by day 7 will be followed up and repeated on day 28 and 42. A specific monitoring of LFT will be performed for any patient in which ALT values are greater than 3xULN combined with a bilirubin greater than 2xULN (Hy's law), or if ALT has risen to above x5ULN, irrespective of other accompanying abnormalities (cf Appendix 2 on "Adverse Event of Special Interest: drugs and the liver"). In such cases, LFT will need to be repeated twice a week until values return to baseline. Hy's law cases will need to be reported as a SAE (See Section 14.2). Total blood volume per time point for biochemistry and haematological assessments will be 2 mL.

*Time windows for follow-up visits:* 

The time-window for the visit on Day 7 is + 1 days, for the visits on Days 14 - 35 is -1 to +1 days and for D42 is -1 to +1 days. If patients do not attend for follow-up a home-visitor from the study team will try to locate the patient and bring them to the clinic.

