The laboratory will have standing orders to analyze the value of ALP isoenzymes in situations where ALP values exceed twice the upper limit of normal. Similarly, the central laboratory will have standing orders to fractionate total bilirubin into its direct and indirect components in situations where the total bilirubin value exceeds 2 times the upper limit of normal.

• The investigator should obtain a hepatitis panel (Anti-HAV IgM, Anti-HBc IgM, HBsAg, and hepatitis C RNA), hepatitis E IgM antibody (if subject outside N. America, or has travelled outside N. America in prior 3 months); cytomegalovirus (CMV) testing polymerase chain reaction (PCR) testing, pp65 antigen, or IgM antibody; Epstein Barr virus (EBV) viral capsid antigen IgM antibody; serum

- creatinine phosphokinase (CPK) and lactate dehydrogenase (LDH). If bilirubin >2 x ULN, bilirubin should be fractionated to obtain % direct bilirubin.
- When ALT >3xULN and bilirubin >2xULN (>35% direct bilirubin on fractionation), obtain: antinuclear antibody, anti-smooth muscle antibody, Type 1 anti-liver kidney microsomal antibodies.

If laboratory values are returned that meet the above described criteria, and if there is a possibility of past or recent exposure to infectious hepatitis, and/or a history of high-risk behaviours that would place the subject at risk for infectious hepatitis.

If laboratory values are returned that meet the above-described criteria, the investigator should attempt to document the following in the investigator comment log of the CRF prior to contacting the sponsor:

- The subject's age, gender and weight.
- The date (and visit number) on which the blood sample was obtained.
- The Randomization date as well as the dose level that the subject is currently taking, and the duration of exposure to that dose level. The exact date on which the subject took the last dose of the study medication and an objective assessment should be obtained of the subject's compliance with the study medication.
- The specific abnormal laboratory values, as well as those of each of the other LFTs noted above (regardless of value) and, when relevant, results of isoenzyme or fractionation analyses. The investigator should also document the corresponding laboratory values at screening/baseline.
- Other notable abnormalities in laboratory values (*e.g.*, complete blood count, eosinophilia, or electrolyte abnormalities, if present).

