Possible Hy's Law case following the FDA Guidance on Drug Induced Liver Injury: Premarketing Clinical Evaluation dated July 2009 A possible Hy's law case is defined as a subject with any value of ALT or AST above 3xULN together with an increase in bilirubin to a value higher than 2xULN and NOT associated to an ALP value higher than 2xULNA decision on medical and scientific grounds is required to assess whether an immediate notification of an event is warranted in other situations, such as medically important events which are not life-threatening, fatal or cause hospitalization, but could endanger the patient or could rendered necessary an intervention to prevent one of the above conditions to develop.

Remark: Examples of such events are intensive care in the emergency room or at home to treat a bronchospasm; a haematological dyscrasia; convulsions or an asymptomatic increase ALT ( $\geq 10 \text{ x ULN}$ ) not causing hospitalisation, or the development of drug addiction or abuse

TABLE 1: STUDY SCHEDULE

	D0	D1	D2	D3	D4	D7	D14	D21	D28	D35	D42	REPf		olumes
Screening													(ml) per time	
Written informed consent	X												adult	Child
Assign participant ID	X												≥16 yrs	<16yrs
Participant's history	X													
Symptoms checklist	X	X	X	X	X	X	X	X	X	X	X	X		
Vital signs	X	X	X	X	X	X	X	X	X	X	X	X		
Temperature	X	X	X	X	X	X	X	X	X	X	X	X		
General Examination	X	X	X	X	X	X	X	X	X	X	X	X		
Study Drug administration														
PYR-Artesunate	X	X	X											
Laboratory Procedures														
#Malaria blood film	X	X	X	X	X	X	X	X	X	X	X	X	0.5	0.5
HCT or Hb	X	X	X	X	X	X	X	X	X	X	X	X	0.03	0.03
Filter paper blots	X											X	0.3	0.3
FBC	X			X		X	X		X		X	X	1	1
Biochemistry	X			X	_	X	X		X		X	X	1	1
	X					X						X	0.5	0.5

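### The main secondary hepatic endpoint cannot be computed in full: conjugated bilirubin is not in the scheduled follow-up panel, and neither it nor alkaline phosphatase has a case report form field

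*Protocol*

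**What the plan says.** Section 3 (Main secondary endpoints) asks for absolute values and "change from baseline related to hepatic biological values (ALT, AST, Total and conjugated bilirubin, alkaline phosphatase"), with other relevant parameters allowed if available, "at day 0, 3, day 7 and day 28 and where available, any additional follow up values to confirm return to baseline values". The Synopsis names the same five analytes and the same four days.

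Three places govern which tests are run:

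- The Enrolment procedures give the day 0 biochemistry as "AST/ALT, bilirubin total/conjugated, alkaline phosphatase", which is all five analytes.
- Section 9 (Follow up) schedules "Blood biochemistry and basic haematology on D0, D3, D7 D14, D28 and D42" and then lists "Tests for: AST/ALT, total bilirubin and alkaline phosphatase". Conjugated bilirubin is not in that list.
- Appendix 1 adds a conditional test. When total bilirubin is above twice the upper limit of normal (ULN), "the central laboratory will have standing orders to fractionate total bilirubin into its direct and indirect components".

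The forms in Appendix 3 govern what is recorded. The liver block is on the day 0, 3, 7 and 28 forms and has four lines: total bilirubin, albumin, ALT and AST. The day 14 form, the form for any other day and the final-day (28/42) form have no liver block. Haemoglobin and haematocrit have a field on the screening form (Appendix 2) only. No form has a field for the full blood count (FBC). Table 1 schedules haematocrit or haemoglobin at every visit, and FBC and biochemistry on days 0, 3, 7, 14, 28 and 42.

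**The concern.** The endpoint, the test list and the forms do not describe the same data. An assay that is not run cannot be restored at analysis, and a result with no field may never reach the database. A statistical analysis plan could not repair either gap.

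This matters because section 17.1 names liver enzyme elevation as the known concern with this drug, and section 12.3 makes hepatotoxicity an event of special interest. The hepatic endpoint is the only one ranked as main secondary. Section 3 also lists change over time in haematological and biochemical parameters as an endpoint. Its scheduled values on days 14 and 42, and all its haematology after screening, have no field.

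**Working it through.** The protocol gives no figure of its own on this point. The check sets the endpoint against the planned tests and the CRF fields, analyte by day.

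Inputs: required analytes and days from section 3; planned tests from the Enrolment procedures (day 0) and section 9 (later days); recorded fields from the Appendix 3 liver blocks. The conditional fractionation in Appendix 1 is not counted, because it does not give a value for every patient.

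| Analyte | Required days | Test planned | CRF field |
|---|---|---|---|
| ALT | 0, 3, 7, 28 | 0, 3, 7, 28 | 0, 3, 7, 28 |
| AST | 0, 3, 7, 28 | 0, 3, 7, 28 | 0, 3, 7, 28 |
| Total bilirubin | 0, 3, 7, 28 | 0, 3, 7, 28 | 0, 3, 7, 28 |
| Alkaline phosphatase | 0, 3, 7, 28 | 0, 3, 7, 28 | none |
| Conjugated bilirubin | 0, 3, 7, 28 | 0 only | none |

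Absolute values:

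- Required: 5 analytes × 4 days = 20.
- Planned tests: 4 × 4 + 1 = 17. The gap is conjugated bilirubin on days 3, 7 and 28.
- CRF fields: 3 × 4 = 12. The gap is 8 of 20, or 40%.

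Changes from baseline (days 3, 7 and 28 against day 0):

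- Required: 5 × 3 = 15.
- Planned tests: 4 × 3 = 12.
- CRF fields: 3 × 3 = 9. The gap is 6 of 15, or 40%.

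Effect of each repair:

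- Fields for both analytes, panel unchanged: 12 + 4 + 1 = 17 of 20 values and 9 + 3 = 12 of 15 changes.
- Fields for both, and conjugated bilirubin in the section 9 panel: 20 of 20 and 15 of 15.
- Alkaline phosphatase field only, and conjugated bilirubin removed from the endpoint: 4 × 4 = 16 of 16 and 4 × 3 = 12 of 12.

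Days 14 and 42 are not endpoint days and contribute nothing to these counts. Their missing block bears on three other things: the values meant to show return to baseline; the section 9 rule that a day 3 ALT elevation not back to baseline by day 7 "will be followed up and repeated on day 28 and 42"; and the endpoint on biochemical change over time. The confirmation tests within 48 hours and the twice-weekly repeats in section 9 fall on unscheduled days, and the form for those days has no liver block.

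**The case against.** **The endpoint is largely intact.** A reader might infer that it cannot be computed at all. The documents do not support that. The liver block is on exactly the four endpoint days, and ALT, AST and total bilirubin are tested and recorded on each. The enzymes behind the named safety concern are fully captured. This objection stands.

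**Hy's law cases are covered.** A reader might also infer that a possible Hy's law case could not be confirmed or ruled out. That does not follow either. Appendix 1 defines a possible case by ALT or AST above 3×ULN with bilirubin above 2×ULN and "NOT associated to an ALP value higher than" 2×ULN. Direct bilirubin is not part of that definition; the 35% direct fraction belongs to a separate statement on significant liver injury. Alkaline phosphatase is tested on every biochemistry day, and bilirubin is fractionated when raised. For triggered cases the investigator is asked to enter all the liver tests, with baseline values, in the CRF comment log. Section 9 has Hy's law cases reported as serious adverse events, and the Appendix 4 form asks for relevant laboratory results. These routes serve individual cases. They do not supply a cohort summary of alkaline phosphatase or conjugated bilirubin.

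**Section 9 may be shorthand.** Its list also covers day 0, where the Enrolment procedures do include conjugated bilirubin, and Table 1 shows one undivided biochemistry row. The laboratory might therefore run conjugated bilirubin throughout. That is possible. The passages then conflict, and the CRF gap remains.

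**Albumin is permitted.** The endpoint allows other relevant parameters, so recording albumin is not an error, although no test list orders it.

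**Conclusion.** The concern holds in limited form. As written, two of the five analytes in the main secondary endpoint have no structured data: 8 of 20 values and 6 of 15 changes from baseline have no CRF field. The two gaps differ in kind. For alkaline phosphatase the gap is in data capture only, since the test is ordered on every endpoint day. For conjugated bilirubin the test itself is also not assured after day 0 unless total bilirubin exceeds 2×ULN.

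Separately, biochemistry on days 14 and 42, unscheduled liver tests and all follow-up haematology have no field. This weakens the return-to-baseline values and the endpoint on laboratory change over time.

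The conclusion assumes that the Appendix 3 forms are the route by which results reach the database. If laboratory results are transferred directly, alkaline phosphatase could be recovered, but the protocol describes no such transfer. Nothing here touches the primary endpoint or requires the hepatic endpoint to be moved to all six biochemistry days. It should be fixed, but it is not a reason to doubt the design.

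**What to change.** Reconcile section 3, the Enrolment procedures, section 9 and Table 1 with the Appendix 3 forms:

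1. Add alkaline phosphatase and conjugated bilirubin to the CRF liver block.
2. Put the block on the day 14, day 42 and any-other-day forms.
3. Add haematocrit or haemoglobin and FBC fields on the days Table 1 schedules them.
4. Either list conjugated bilirubin in the section 9 panel, or remove it from the endpoint in section 3 and the Synopsis. If it is removed, its new CRF field is not needed for this endpoint.

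Items 1 to 3 cost a form revision, because the tests are already ordered apart from conjugated bilirubin after day 0. Keeping conjugated bilirubin under item 4 adds one assay on blood already drawn; removing it costs only a text change. The revision belongs before first enrolment, since values not measured or recorded at follow-up may not be recoverable later.

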#### Other secondary endpoints:

- The numbers of patients with a positive malaria slide 72 hours after treatment initiation in each group
- Fever clearance time (i.e. the time taken for tympanic temperature to fall below 37.5°C and remain there for at least 24 hours)
- Kaplan Meier analysis over 28 and 42 days for recrudescence, reinfections and new infections
- PCR uncorrected ACPR at D28 and D42
- 28 and 42 day PCR corrected ACPR
- Gametocyte carriage rates and gametocyte clearance times in each treatment arm
- Documented AEs and SAEs and relationships to study drugs.
- Adverse events in both study arms

• Changes in haematological and biochemical parameters over time.

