#### 6.1 Inclusion Criteria:

- Adults and children  $\geq 20 \text{ kg}$
- Symptomatic of malaria infection, i.e: history of fever within 24 hours and/or presence of fever >37.5°c.
- Microscopic confirmation of asexual stages of *P. falciparum* (mixed infection in Pailin) any parasite below 150,000/asexual per micro litre
- Ability to take oral medication.
- Written informed consent given to participate in the trial given by the patient or in case of children <16 years their attending guardian.

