# Early treatment failure

- danger signs or severe malaria on day 1, 2 or 3 in the presence of parasitaemia;
- parasitaemia on day 2 higher than on day 0, irrespective of axillary temperature;
- parasitaemia on day 3 with axillary temperature ≥ 37.5 °C;

• parasitaemia on day  $3 \ge 25\%$  of count on day 0.

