#### (Late treatment failure)

# Late clinical failure

- danger signs or severe malaria in the presence of parasitaemia on any day between day
   4 and day 28 (day 42) in patients who did not previously meet any of the criteria of
   early treatment failure;
- presence of parasitaemia on any day between day 4 and day 42 with axillary temperature ≥ 37.5 °C or history of fever in patients who did not previously meet any of the criteria of early treatment failure

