#### Late parasitological failure

 presence of parasitaemia on any day between day 7 and day 42 with axillary temperature < 37.5 °C in patients who did not previously meet any of the criteria of early treatment failure or late clinical failure

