# **APPENDIX 2. CASE SCREENING FORM**

Case screening	ng form
Hospital name:	Study number:
Locality:	Patient screening number:
District:	Date of visit (dd-mmm-yyyy):
Province:	Date illness started (dd-mmm-yyyy):
Demographi	c data
Date of birth (dd-mmm-yyyy): or est years	imated age: in: months or
Height (cm): Weight (kg):	
Sex: Male Female	
If female, is the patient pregnant?   Yes   No	Not sure
If pregnant, provide the date of the last menstrual pe	eriod (dd-mmm-yyyy):
Pre-treatment te	mperature
History of fever in previous 24 h?  Yes  No	
Temperature: °C  Axillary Tympanic [	Rectal Oral
Thick and thin blood smears for estimati	on of P. falciparum parasite counts
Species: P. falciparum P. vivax P.f mixed	d+ non-P.f species
Were species other than P. falciparum present?	Yes No (If yes, patient is not eligible).
Approximate number of P. falciparum asexual para Presence of $1-100$ parasites / $3-6$ white blood cells' eligible )	
Presence of P. falciparum gametocytes?  Yes	No
Has a blood sample for PCR been collected?  Ye	s 🗌 No
Haemoglobin: g/dl Haematocrit:	%
Urinary analysis (pregnancy	test for female patients)
Result of pregnancy test:  Positive  Negative (	If positive, patient is not eligible)
Inclusion cr	riteria

 
age between and months/ye
 
mono-infection with P. falciparum confirminfection)
 
	ned by positive blood smear (i.e. no mixed
• parasitaemia between and and	/μl of asexual forms

 
measured temperature (depending on metho within previous 24 h
 
	d of measurement) or history of fever

 
ability to swallow oral medication
 
	

 
ability and willingness to comply with the st
 
	tudy protocol for the duration of the study

and to comply with the study visit schedule					
• absence of severe malnutrition (defined as per protocol)					
Does the patient meet all the inclusion criteria?	Yes No (If no, patient is not eligible)				
Case screening	form (page 2)				
Exclusion	criteria				
• signs and symptoms of severe or complicate according to WHO criteria (Appendix 1)	ated malaria requiring parenteral treatment				
• mixed or mono-infection with another Pla	smodium species detected by microscopy				

 
severe malnutrition
 
					

 
febrile conditions caused by diseases other than malaria or other known underlying chronic or severe diseases
 
					

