Presence of danger signs or signs or	f severe or co	mplicated malari	ia?  Yes  No	
If yes, perform thick blood smear.				
Temperature: °C  Axillar	y 🔲 Tympani	c Rectal 0	Oral	
Thick blood smears	for estimatio	n of P. falciparu	m parasite counts	S
Average number of asexual P. falc.	iparum parasit	tes/µl:		
Presence of P. falciparum gametoc	ytes?  Yes	☐ No		
Were species other than P. falcipar	um present?	Yes No		
If yes, which species?   P. falcipe	arum 🔲 P. vi	vax P.f mixed	d+ non-P.f species	
	Advers	e events		
Presence of an adverse event?	Yes No			
If yes, name the adverse event:				
Is it a serious adverse event? \( \subseteq \text{ Y} \)	es 🗌 No. If y	es, inform the sp	onsor.	
	Medication a	dministration		
Name(s) of antimalarial drug(s)	Time of dose (hh:min)	Number of tablets	Did the patient vomit?	Time of vomiting (hh:min)
			☐ Yes ☐ No	
☐ Yes ☐ No				
Name(s) of other medicine(s)			1	
, ,			☐ Yes ☐ No	
			☐ Yes ☐ No	

Case report form: follow-up day 2					
Study number:					
Patient identity number:					
Date of visit (dd-mmm-yyyy)	:				
	Clinica	ıl status			
Presence of danger signs or si	gns of severe or co	mplicated malari	ia? 🗌 Yes 🔲 No		
Temperature: °C \sum A:	xillary 🗌 Tympani	ic 🗌 Rectal 🔲 (	Oral		
Thick blood sm	ears for estimatio	n of P. falciparu	m parasite counts	5	
Average number of asexual P	. falciparum parasi	tes/μl:			
Presence of P. falciparum gar	netocytes?  Yes	☐ No			
Were species other than P. fai	lciparum present? [	Yes No			
If yes, which species? $\square$ P. f.	alciparum 🗌 P. vi	vax P.f mixed	d+ non-P.f species		
	Advers	e events			
Presence of an adverse event?	Yes No				
If yes, name the adverse even	t:				
Is it a serious adverse event? [	Yes No. If y	es, inform the sp	onsor.		
	Medication a	dministration			
Name(s) of antimalarial drug(s)	Time of dose (hh:min)	Number of tablets	Did the patient vomit?	Time of vomiting (hh:min)	
			☐ Yes ☐ No		
☐ Yes ☐ No					
Name(s) of other medicine(s)					
			☐ Yes ☐ No		
			☐ Yes ☐ No		

Case report form: follow-up day 3
Study number:
Patient identity number:
Date of visit (dd-mmm-yyyy):
Clinical status
Presence of danger signs or signs of severe or complicated malaria?   Yes   No
Temperature: °C Axillary Tympanic Rectal Oral
Thick blood smears for estimation of P. falciparum parasite counts
Average number of asexual P. falciparum parasites/µl:
Presence of P. falciparum gametocytes?    Yes    No

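### Failure rules need an axillary temperature, fever clearance needs a tympanic one, and each visit form has one entry by any of four routes, so failure status on days 3 to 6 can be undefined.

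*Protocol*

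**What the plan says.** The protocol deals with temperature in four places.

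- **Fever clearance** (Synopsis, and section 3, Other secondary endpoints): the time taken for "tympanic temperature to fall below 37.5°C", sustained for at least 24 hours.
- **Treatment failure** (section 10): early treatment failure includes "parasitaemia on day 3 with axillary temperature ≥ 37.5 °C". Late clinical failure includes "presence of parasitaemia on any day between day 4 and day 42 with axillary temperature ≥ 37.5 °C or history of fever". Late parasitological failure is "presence of parasitaemia on any day between day 7 and day 42 with axillary" temperature below 37.5 °C.
- **Inclusion** (Synopsis and Inclusion Criteria): "history of fever within 24 hours and/or presence of fever >37.5°c", with no route named.
- **Data capture** (Appendices 2 and 3, Table 1): the screening form and every visit form carry a single line, "Temperature: °C Axillary Tympanic Rectal Oral", and the schedule has a single temperature row. The screening form acknowledges that the measured temperature depends on the method, but gives no values by method.

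No section says which route is to be used at visits, requires the same route within a patient, or says how a reading by another route is to be handled.

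**The concern.** Fever clearance and treatment failure are assessed at the same visits on the same patients, yet they call for different routes, and the form has room for one reading. A site that follows section 3 and measures tympanically records nothing to which the axillary rules of section 10 can be applied. Someone must then either treat that reading as if it were axillary or leave the criterion unassessed. The protocol supports neither choice.

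This matters most among slow clearers, since the temperature rules bite only when parasites are still present. The Background section reports prolonged clearance in western Cambodia and slower clearance on this drug in Pailin. The purpose of the trial is to learn whether the lower efficacy seen there was chance or real. A patient who is slide-positive on day 3 can be a failure or not according to one temperature reading, and Appendix 5 counts early treatment failure as failure in both the PCR-corrected and the uncorrected results. Genotyping cannot correct a misclassification there.

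**Working it through.** **Planned precision.** Section 5 gives an assumed efficacy of 90%, a half-width of 5 percentage points and 138 patients. With n = z²p(1−p)/d² and z = 1.96 (two-sided 95% confidence, assumed because the protocol does not state it):

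n = 1.96² × 0.90 × 0.10 / 0.05² = 138.3, which reproduces 138. Adding 5% gives 138 × 1.05 = 144.9, which reproduces 145. The sample size is not in question here. It only sets the scale.

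**Where the route can change the efficacy result.** This follows from reading section 10 against Appendix 5.

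1. *Day 2.* The rule is "parasitaemia on day 2 higher than on day 0, irrespective of axillary temperature". The route has no effect.
2. *Day 3.* Of the four early-failure criteria, only parasitaemia with fever uses a temperature threshold. Danger signs, the day-2 count and a day-3 count of at least 25% of day 0 do not. A patient is exposed if slide-positive on day 3, below 25% of the day-0 count, without danger signs, and with a temperature that falls on different sides of 37.5 °C by different routes. The day-3 rule has no history-of-fever alternative, so the thermometer alone decides.
3. *Days 4 to 6.* Late clinical failure starts on day 4, but late parasitological failure starts only on day 7. Parasitaemia with fever is a failure, and afebrile parasitaemia is not yet one. Section 9 asks for daily smears in the first week until clearance, so slow clearers can be seen in this window. Appendix 5 counts late clinical failure before day 7 as failure with no genotyping step. A history of fever or danger signs also meets the definition, whatever the thermometer shows.
4. *Day 7 onward.* A parasitaemic patient is a late clinical failure at or above 37.5 °C or with a history of fever, and otherwise a late parasitological failure. Appendix 5 puts both on one row with the same PCR handling. The route changes the reported split between the two. It does not change ACPR or the Kaplan-Meier result.
5. *ACPR on day 42.* It does not depend on temperature that day, but it excludes anyone who failed earlier, so it inherits items 2 and 3.

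**Scale.** Each patient whose failure status changes moves efficacy by 1/138 = 0.72 percentage points. Three patients move it 3/138 = 2.2 points, five move it 5/138 = 3.6, and seven move it 7/138 = 5.1, about the whole planned half-width.

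**Illustration on assumed inputs.** The documents give neither the day-3 positivity rate nor the share of those patients whose fever status differs by route. Suppose the first is 10% to 40% and the second 2% to 10%. The number reclassified then runs from 138 × 0.10 × 0.02 = 0.3 patients (0.2 points) to 138 × 0.40 × 0.10 = 5.5 patients (4.0 points). This shows how strongly the answer depends on the inputs. It is not an estimate.

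**The case against.** The strongest reply is that the failure definitions are consistent with one another. Each temperature-based rule names axillary temperature, so read literally a tympanic reading never satisfies it. The visit forms carry no 37.5 °C value, they record the route, and they look like generic templates, with age and parasitaemia limits left blank. Using a different route for a separate secondary endpoint is not in itself a contradiction.

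Much of this stands. A reader might infer that the protocol tells sites to apply one cut-off to every route, or that sites will use different routes. No section says either. What remains is that the form has one entry, so meeting the fever-clearance definition can leave the failure definition without its input. Recording the route lets such visits be found afterwards, but it cannot recover an axillary value.

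A reader might also infer that early and late clinical failure as a whole, and so the efficacy result throughout follow-up, depend on the thermometer. Section 10 and Appendix 5 do not support that beyond day 6.

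Finally, a reader might put a large figure on the effect. Assume that tympanic readings run 0.3 to 0.4 °C above axillary, that axillary temperature in day-3-positive patients has mean 36.8 °C and SD 0.5 °C, and that 20% to 40% are day-3 positive. The shift then comes to about 2.6 to 7.7 points. None of these inputs is in the documents. The calculation also supposes that every reading switches route and that nobody reclassified would have failed anyway. At its upper end, 27.4% of the 40% who are positive would be early failures by this one criterion. That is 0.40 × 27.4% = 11.0%, or about 16 of 145 patients, which exceeds the 10% total failure implied by the assumed 90% efficacy and the 10 treatment failures assumed in the section 20 budget. The range should not be used.

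**Conclusion.** The inconsistency is real, and its reach is limited. Section 10 requires an axillary reading, section 3 requires a tympanic one, and the visit form holds one reading by any of four routes. A visit recorded by another route cannot be classified under the temperature criteria as written. The primary PCR-corrected result is exposed on day 3 and on days 4 to 6 only. After that, the effect is confined to the descriptive split of late failures.

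The documents give no basis for estimating the size. The figure of about 0.7 points per reclassified patient assumes 138 evaluable patients and no later failure in that patient for another reason. Severity is minor to moderate. The number of patients affected may be small, but the missing readings cannot be reconstructed, so the matter should be settled before enrolment.

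**What to change.** Reconcile the Synopsis, section 3, the Inclusion Criteria, section 10 and the forms in Appendices 2 and 3, in one of two ways:

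- state one measurement route for all visits and all sites, use it in every definition, and leave only that route on the forms; or
- if tympanic temperature is kept for fever clearance, record it in a separate field and classify failure only from the axillary reading that section 10 already specifies.

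Neither option needs a new threshold. The first costs wording and an edit to one form field. The second also adds a field and a second temperature reading at visits where both definitions apply. No extra patients are needed and the analysis does not change.
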